6.3.8 Optional dose tapering strategy in the event of discontinuation

When a decision is made to permanently discontinue ruxolitinib therapy for reasons other than for hematologic safety, a dose tapering strategy may be considered, based on evaluation of the condition of the patient, the current dosing regimen and the clinical judgment of the investigator. If considered to be medically necessary, the investigator may use any treatment to manage withdrawal from ruxolitinib including a gradual tapering of the study drug dosage or use of other medications to manage events occurring after discontinuation.

Short-term courses of corticosteroids have been used in patients with MF and may be considered as part of a tapering strategy. Corticosteroids may be started prior to, or concurrent with, ruxolitinib tapering. When a decision has been made to discontinue the patient utilizing

a tapering strategy, routine study visits and study assessments should continue to be completed per the protocol schedule (see [Table 7-1](#)) until the patient completes the ruxolitinib tapering, regardless of any concomitant medications. The follow-up phone call (30 days post last dose) should also occur as scheduled.

6.4 Concomitant medications

The patient must be told to notify the investigational site about any new medications he/she takes after the start of the study drug. All medications (other than study drug) and significant non-drug therapies (including physical therapy, and herbal/natural medications) administered during the study must be listed on the Concomitant Medications/Significant Non-Drug Therapies of the eCRF. All prior medications used to treat Polycythemia vera will be recorded. Patients will be instructed not to take any additional medications (including over-the-counter products) during the course of the study without consultation with the investigator.

6.4.1 Permitted concomitant therapy

6.4.1.1 Hormonal contraception

Females of childbearing potential will be allowed to use oral, injectable or implanted contraceptives that have been determined to be at least 99% effective as indicated in Exclusion Criterion (see [Section 5.3](#)).

6.4.2 Permitted concomitant therapy requiring caution and/or action

The following medications have restrictions on use, dose, or require changes to the way in which ruxolitinib is administered during the study:

- Systemic corticosteroid doses greater than the equivalent of 10 mg prednisolone per day is not permitted, unless used as part of a ruxolitinib-dose tapering strategy (see [Section 6.3.8 Optional dose tapering strategy in the event of discontinuation](#))
- Low dose aspirin (75-150 mg/day) and non-steroidal anti-inflammatory agents (acetaminophen, ibuprofen) may be used. Higher doses of aspirin (> 150 mg/day) should not be used except when medically indicated and recommended by the treating physician.
- When concomitant administration of an anticoagulant/antiplatelet medication is required for patient management, the platelet count history, and any observations of thrombocytopenia during the study while on study drug should be considered.
- Granulocyte growth factors are not allowed while study medication is being administered but may be used for severe neutropenia at the Investigator's discretion while study medication is being withheld.
- Inducers or inhibitors of the metabolizing enzyme CYP3A4 (Refer to [Appendix 7](#)):
- When concomitant administration of a strong (potent) systemic inhibitor of CYP3A4 metabolizing enzymes or dual CYP2C9/CYP3A4 inhibitors (see [Appendix 7](#)) is required for patient management, the dose of study treatment must be reduced by approximately 50% to be administered twice daily by decreasing the twice daily dose or by decreasing the frequency of dosing to the corresponding once daily dose when twice daily dosing is not practical.

- Note: No dose adjustment of ruxolitinib is needed for use with topical ketoconazole.
- Note: More frequent monitoring of hematology parameters and clinical signs and symptoms of ruxolitinib related adverse reactions is recommended upon initiation of a strong (potent) CYP3A4 inhibitor.
- No dose adjustment will be made when moderate systemic CYP3A4 inducers (See [Appendix 7](#)) are co-administered with study treatment.

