6.1.1 Dosing regimen

The starting dose of ruxolitinib will be 10 mg bid (see [Section 6.3.4](#) and [Section 6.3.7](#) for exceptions). A standardized dosing paradigm will be used to determine dose adjustments for safety and efficacy so that each patient is titrated to their most appropriate dose (see [Section 6.3.1](#) of the protocol). The ruxolitinib dose should not exceed 25 mg bid and should not be less than 5 mg once a day unless there is an adverse event that warrants interruption.

Patients may self-administer daily ruxolitinib tablets qd or bid (see [Section 6.3.4](#) and [Section 6.3.7](#) for exceptions) orally, without regard to food, in an outpatient setting in accordance with the specified dosing schedule provided by the investigator.

Patients who miss a dose should be counseled to take the next dose as scheduled and not to take double the dose.

Table 6-1 Dose and treatment schedule

| Study treatments | Pharmaceutical form and route of administration | Dose | Frequency and/or Regimen |
|--------------------|---|--|--|
| INC424/ruxolitinib | Tablet for oral use | Starting dose 10 mg bid (approximately 12 hours apart: morning and night), to be increased or decreased (5 mg steps) per standardized dosing paradigm and not to exceed 25 mg bid (see Section 6.1.1) | Daily, unless instructed to temporarily withhold dosing for safety |

The investigator will instruct the patient to take the study drug as per protocol. All dosages prescribed and dispensed to the patient and all dose changes during the study should be recorded on the Dosage Administration Record eCRF.

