6.3.7 Dose reduction for concomitant CYP inhibitor use

Ruxolitinib is metabolized in the liver by the cytochrome (CYP) P450 metabolizing enzyme system, predominantly by the CYP 3A4 isozyme. With concomitant dosing of potent CYP3A4 inhibitors such as systemic ketoconazole, plasma exposure of ruxolitinib increases by approximately 2-fold. Thus, a dose reduction of ~ 50% for ruxolitinib is appropriate for patients who take systemic ketoconazole or other potent CYP3A4 inhibitors systemically as concomitant medication (see [Appendix 7](#)).

Potent inhibitors of CYP3A4 include systemic ketoconazole, clarithromycin, itraconazole, nefazodone and telithromycin. The use of these agents on Study Day 1 will require that patients initiate ruxolitinib therapy at 10 mg qd.

NOTE: once the course of therapy using a potent CYP3A4 inhibitor has been completed, the patient may resume his/her prior bid dose regimen of ruxolitinib beginning the next day.

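### Section 6.3.7 leaves out the dual CYP2C9/CYP3A4 inhibitors for which 6.4.2 requires a halved dose, so a Day 1 fluconazole user can be started on 20 instead of about 10 mg/day

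*Protocol*

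**What the plan says.** **Starting dose.** Section 6.1.1 states: "The starting dose of ruxolitinib will be 10 mg bid". Sections 2.3, 4.1 and 6.3.1 say the same. All four refer to 6.3.4 and 6.3.7 for exceptions and to nothing else. Section 6.3.4 starts patients with platelets of 50 to <100 x 10^9/L at 5 mg bid.

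**Section 6.3.7.** The reduction of about 50% is for patients who take "systemic ketoconazole or other potent CYP3A4 inhibitors systemically as concomitant medication", with a reference to Appendix 7. Five potent agents are then named, followed by the Day 1 rule: "The use of these agents on Study Day 1 will require that patients initiate ruxolitinib therapy at 10 mg qd". A closing note deals with the end of inhibitor treatment: "once the course of therapy using a potent CYP3A4 inhibitor has been completed, the patient may resume his/her prior bid dose regimen". Dual inhibitors and fluconazole are not mentioned.

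**Section 6.4.2.** When a "strong (potent) systemic inhibitor of CYP3A4 metabolizing enzymes or dual CYP2C9/CYP3A4 inhibitors" is needed, "the dose of study treatment must be reduced by approximately 50" per cent. This is done by lowering the twice-daily dose or by "decreasing the frequency of dosing to the corresponding once daily dose when twice daily dosing is not practical".

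**Appendix 7.** Fluconazole is the only dual inhibitor named and is classed as moderate for CYP3A. Doses of 200 mg daily or more are to be avoided, or discussed with the sponsor if clinically necessary. The entry then refers to 6.4.2.

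**Eligibility.** Exclusion 5 bars only strong CYP3A4 inhibitors and inducers at screening.

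**The concern.** The four places that fix the first dose send the reader to 6.3.7 for CYP inhibitors, and 6.3.7 is narrower than the rule in 6.4.2. A fluconazole user meets no exception in the text a site would use to set the first dose, yet falls under a mandatory reduction elsewhere. The consequence is an unreduced first dose of a myelosuppressive drug.

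A second weakness lies in 6.3.7 itself. Its Day 1 dose is a fixed 10 mg qd, whatever start would otherwise apply. Repairing the omission by adding fluconazole to the list would carry that weakness over.

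**Working it through.** All figures are nominal daily doses. The documents give no exposure figure for fluconazole.

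**1. Section 6.3.7's own figure.** Usual start: 10 mg x 2 = 20 mg/day. Day 1 dose with a potent inhibitor: 10 mg x 1 = 10 mg/day. Reduction: 1 - 10/20 = 50%. This agrees with the stated reduction of about 50%.

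**2. Does 6.3.7 reach fluconazole?** Its reduction rule, Day 1 rule and resume note all concern potent CYP3A4 inhibitors. Appendix 7 puts fluconazole in the moderate class. On its wording, 6.3.7 does not apply. Exclusion 5, which is limited to strong agents, does not remove the patient either.

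**3. Dose under each text for a Day 1 fluconazole user.**

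| Start that would otherwise apply | Starting-dose text and wording of 6.3.4/6.3.7 | Section 6.4.2 (x 0.5) | Ratio |
|---|---|---|---|
| 10 mg bid | 20 mg/day | about 10 mg/day (5 mg bid or 10 mg qd) | 20/10 = 2 |
| 5 mg bid (6.3.4) | 10 mg/day | about 5 mg/day | 10/5 = 2 |

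**4. Would it be enough to add fluconazole to 6.3.7's list?** The flat Day 1 dose is 10 mg/day.
- Against the usual start: 1 - 10/20 = 50%.
- Against the 6.3.4 start: 1 - 10/10 = 0%.

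The flat dose therefore gives no reduction to patients who enter with low platelets. The same holds for a potent inhibitor begun between screening and Day 1, a gap of up to 35 days.

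**5. Can a halved dose be given in the low-platelet group?** Half of 5 mg bid is 2.5 mg bid, which does not fit the 5 mg steps in Table 6-1. The once-daily option in 6.4.2 gives 5 mg qd = 5 mg/day. That equals the minimum in 6.1.1, where the dose "should not be less than 5 mg once a day", so it is allowed.

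**6. The resume note.** It returns the patient to the earlier twice-daily regimen. A patient who takes the inhibitor on Day 1 has no earlier regimen, so the note gives no dose to move to.

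**The case against.** **The rule already exists.** Section 6.4.2 applies throughout the study, Day 1 included, and is mandatory. Section 6.3.7 refers to Appendix 7, which refers on to 6.4.2. The unreduced dose arises only if a site stops at the wording of 6.3.7. This is right as far as it goes: the intent is clear, and no text orders a full dose for fluconazole users. But the path takes two steps. In Appendix 7 the reference to 6.4.2 directly follows the sentence about fluconazole at 200 mg daily or more, so a site treating below that dose could think it does not apply. Those are mainly the patients affected.

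**The group is very small.** Exclusion 6 bars active infection needing therapy, exclusion 7 bars HIV and immunodeficiency, and the higher fluconazole doses are restricted. This stands. What remains is mainly prophylaxis below 200 mg/day or fluconazole begun after screening. Medications are recorded from screening, so a site can see the use before Day 1.

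**Harm is not shown.** This also stands. As a bounding assumption, suppose fluconazole had the full twofold effect that 6.3.7 gives for potent inhibitors. Then 10 mg bid would resemble 20 mg bid. That is above the 10 mg bid maximum for Weeks 1 to 4 in Table 6-2 but below the 25 mg bid ceiling. Four-weekly visits and the count-based rules in 6.3.2 limit how long any excess lasts.

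**The flat 10 mg qd is a separate matter, already answered by 6.4.2.** Section 6.4.2 does yield 5 mg qd for a low-platelet starter. However, 6.3.7 states a different dose for Day 1 potent-inhibitor users, and any repair that adds dual inhibitors to that sentence would inherit it.

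**An amendment may come too late.** Section 4.1 ends treatment by 31 December 2017 at the latest, and the SAP amendment is dated 13 March 2018. If that limit was kept, new wording would reach no patient in this study. That bears on the practical use of the correction. The texts still disagree.

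**Conclusion.** The concern holds. For the same patient, the starting-dose text and 6.4.2 lead to different first doses: 20 against about 10 mg/day at the usual start, and 10 against about 5 mg/day at the low-platelet start, a factor of 2 in each case. In addition, the flat Day 1 dose in 6.3.7 is a 0% cut for a patient starting under 6.3.4.

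The factor of 2 refers to nominal dose and assumes a site that works from the starting-dose text and the wording of its two cited exceptions. Any excess lasts only while fluconazole continues or until the dose is corrected. The documents give no count of affected patients. This is a minor safety inconsistency that should be corrected. It has no material effect on the trial's descriptive results.

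**What to change.** Amend 6.3.7 as follows.

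- Extend the reduction rule and the Day 1 rule to dual CYP2C9/CYP3A4 inhibitors, with fluconazole as the example, and cite 6.4.2.
- Replace the flat Day 1 dose with one rule for all covered inhibitors: half the start that would otherwise apply. That is 5 mg bid, or 10 mg qd where twice-daily dosing is not practical, and 5 mg qd for patients starting under 6.3.4.
- Extend the resume note to dual inhibitors. State that Day 1 users move to the start that would otherwise have applied (10 mg bid, or 5 mg bid under 6.3.4), blood counts permitting.
- Keep the Appendix 7 requirement for sponsor consultation at fluconazole 200 mg/day or more.

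The four starting-dose sections already cite 6.3.7 and need no change. The column heading of Table 6-2, which also mentions only potent inhibitors, could be aligned at the same time.

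The cost is wording in one section of a protocol amendment, with the approvals that section 12.1 requires. No new data or procedures are needed.

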6.4.3 Prohibited concomitant therapy

The following medications are prohibited during the study until treatment discontinuation:

- a. Any investigational medication (other than ruxolitinib) that is not approved for any indication. Use of such medications within 30 days or 5 half-lives, whichever is longer, prior to the first dose of study drug and during the study through the Safety Follow-up Visit is prohibited.
- b. Use of PEG-IFN-alpha-2a within the 5 weeks prior to Study Day -1 is prohibited.
- c. Use of any medication to treat PV disease (except for low-dose aspirin) is prohibited once dosing with ruxolitinib begins on or after Study Day 1.
- d. Use of ³²P prior to or during the study until treatment discontinuation at any time is prohibited.
- e. Use of busulfan or chlorambucil during the study until treatment discontinuation at any time is prohibited.

Aspirin in doses exceeding 150 mg per day is prohibited unless medically indicated.

6.5 Patient numbering, treatment assignment or randomization

6.5.1 Patient numbering

Each patient is identified in the study by a Patient Number that is assigned when the patient is first enrolled for screening and is retained as the primary identifier for the patient throughout his/her entire participation in the trial. The Patient No. consists of the Center Number (Center No., as assigned by Novartis to the investigative site) with a sequential patient number suffixed to it, so that each patient is numbered uniquely across the entire database. Upon signing the informed consent form, the patient is assigned to the next sequential Patient No.

The investigator or designated staff will contact the IRT and provide the requested identifying information for the patient to register them into the IRT. Once assigned, the Patient Number must not be reused for any other patient and the Patient Number for that individual must not be changed, even if the patient is re-screened. If the patient fails to be dosed, the reason will be entered into the Screening Log page.

6.5.2 Treatment assignment

Prior to dosing, all patients who fulfill all entry criteria will be assigned to treatment via IRT. The investigator or his/her delegate will contact the IRT and confirm that the patient fulfills the protocol's entry criteria.

6.5.3 Treatment blinding

Not applicable.

6.6 Study drug preparation and dispensation

The investigator or responsible site personnel must instruct the patient or caregiver to take the study drugs as per protocol. Study drug(s) will be dispensed to the patient by authorized site personnel only. All dosages prescribed to the patient and all dose changes during the study must be recorded on the Dosage Administration Record CRF

Table 6-5 Preparation and dispensing

| Study treatment | Dispensing | Preparation |
|------------------------|--|--------------------|
| INC424/ruxolitinib | Tablets including instructions for administration are dispensed by study personnel on an outpatient basis. Patients will be provided with adequate supply of study drug for self-administration at home until their next scheduled study visit. | Not applicable |

6.6.1 Study drug packaging and labeling

INC424/ruxolitinib can be provided as global supply or as local commercial material where appropriate and per local regulation. If INC424/ruxolitinib is sourced and labeled in-country, the locally approved form and packaging will be used.

Medication labels will be in the local language and comply with the legal and regulatory requirements of each country. Labels will include storage conditions for the drug but no information about the patient.

6.6.2 Drug supply and storage

INC424/ruxolitinib treatments must be received by designated personnel at the study site, handled and stored safely and properly, and kept in a secured location to which only the investigator and designated site personnel have access. Upon receipt, the *study treatment* should be stored according to the instructions specified on the drug labels and in the Investigator's Brochure.

6.6.3 Study drug compliance and accountability

6.6.3.1 Study drug compliance

Compliance will be assessed by the investigator and/or study personnel at each patient visit and information provided by the patient and/or caregiver will be captured in the Drug Accountability Form. This information must be captured in the source document at each patient visit.

Sites should counsel patients if patient compliance falls below 80% of the prescribed dose.

6.6.3.2 Study drug accountability

The investigator or designee must maintain an accurate record of the shipment and dispensing of study treatment in a drug accountability log. Drug accountability will be noted by the field

monitor during site visits and at the completion of the study. Patients will be asked to return all unused study treatment and packaging on a regular basis, at the end of the study or at the time of study treatment discontinuation.

At study close-out, and, as appropriate during the course of the study, the investigator will return all used and unused study treatment, packaging, drug labels, and a copy of the completed drug accountability log to the Novartis monitor or to the Novartis address provided in the investigator folder at each site.

6.6.3.3 Handling of other study treatment

Not applicable.

6.6.4 Disposal and destruction

The study drug supply can be destroyed at the local Novartis facility, Drug Supply group or third party, as appropriate

7 Visit schedule and assessments

7.1 Study flow and visit schedule

Table 7-1 lists all of the assessments and indicates with an “X”, the visits when they are performed. All data obtained from these assessments must be supported in the patient’s source documentation.

All visits are to be scheduled according to the appropriate number of calendar days from Day 1 of ruxolitinib drug administration. There is a visit window of +/- 7 for visits up to Week 24 and +/- 14 days for visits after.

Note: If treatment with ruxolitinib is withheld at any time, all study visits, and safety assessments should continue according to the appropriate number of calendar days from Day 1 as per the schedule of assessments.

All data obtained from these assessments must be supported in the patient’s source documentation. No eCRF will be used as a source document except for the MPN-SAF TSS. The table indicates which assessments produce data to be entered into the database (D) or remain in the source documents (S).

Table 7-1 Visit evaluation schedule

7.1.1 Screening

Written informed consent must be obtained before any study specific procedure is performed. Screening assessments to confirm eligibility should be performed as per the schedule of assessments in [Table 7-1](#).

All assessments should be completed within the 35 day screening period.

Re-screening of patients will be allowed, if all entry criteria are not met during the screening period (-35 days to -1 day).

7.1.1.1 Eligibility screening

Patients must meet all inclusion ([Section 5.2](#)) and none of the exclusion ([Section 5.3](#)) criteria during the Screening phase in order to be eligible to proceed to the Treatment Phase of the study. Patient eligibility will be confirmed by using the following processes:

- Investigative staff will capture patient eligibility within the source documents maintained at the site,
- All screening assessment results must be received and reviewed by the investigator/designee to be within protocol required parameters before the patient starts study treatment,
- Patient eligibility will be confirmed by the site within the IRT system. Following registering in IRT for screening, patient eligibility will be checked once all screening procedures are completed. The eligibility check will be embedded in the IRT system. An end of screening phase disposition will be completed. Please refer and comply with detailed guidelines in the IRT manual. Only when eligibility has been confirmed will the IRT system indicate patient can proceed with study treatment.

Additionally, sites will enter patient information into the eCRF, and automated queries will be generated for immediate resolution should patient eligibility be in question based on the patient information entered.

7.1.1.2 Information to be collected on screening failures

A patient who signs an informed consent but fails to satisfy all eligibility criteria for any reason will be considered a screen failure. The reason for not starting dosing will be entered on the Screening Phase Disposition Page. The demographic information, informed consent, and Inclusion/Exclusion pages must also be completed for Screen Failure patients. No other data will be entered into the clinical database for patients who are screen failures, unless the patient experienced a Serious Adverse Event during the Screening Phase (see [Section 8](#) for SAE reporting details).

Patients who signed ICF but are considered ineligible after signing the study consent will be considered as screening failures, and data will be handled in the same manner.

The following eCRFs must be completed for screening failure patients:

- Screening Phase Disposition page (including reason for not satisfying eligibility criteria and being started on treatment)

- Informed consent
- Demography
- Adverse Events (only if an SAE occurs)
- Inclusion/Exclusion Criteria

In order to be officially considered a screen failure, the IRT system should be notified, preferably within 2 days of the decision to screen fail the patient.

